### **2.1.3. Exploratory Objectives**

- Evaluate whether response to nivolumab treatment is enriched among patients with tumor programmed death-ligand 1 (PD-L1) expression on tumor cells and on tumor-infiltrating lymphocytes and antigen-presenting cells (APCs)
- Identify genomic biomarkers associated with response to nivolumab
- Evaluate correlations between alterations in DNA-damage-repair genes and PD-L1 expression
- Evaluate correlations between tumor-infiltrating lymphocytes and APCs with response to nivolumab
- Evaluate subtypes of “exhausted” tumor-infiltrating lymphocytes
- Explore whether peripheral T-cells are present that might recognize tumor neoantigens and whether these correlate with responses to nivolumab
- Assess for genomic alterations in circulating tumor DNA and correlate with mutations identified in primary tumor specimens
- Assess levels of plasma cytokines prior to initiation and during therapy and determine whether levels or changes in specific cytokines may be predictive biomarkers for response
- Assess PBMC subsets prior to initiation and during therapy and determine basal features or changes during therapy may be predictive biomarkers for response

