## 7. STUDY CALENDAR & EVALUATIONS

Event	Screening	On Treatment (28-day cycles)	End of Study i	Follow-Up
	≤ 28 days prior to enrollment	Day 1 j	Within 30 days of last dose	Every 3 months until mPCa
Informed consent	X			
Confirmation of all eligibility criteria	X k			
Medical history a	X		X	X l
Prior systemic and radiation therapy b	X			
Physical examination c	X	X	X	
ECOG performance status	X	X	X	
Concomitant medication review	X	X	X	
Adverse Event review	X	X	X	X l (100 days after last nivolumab dose)
Chemistries d	X	X		
Hematology d	X	X		
TSH (with reflex free T4 testing if abnormal)	X	X		
Prostate-specific antigen e	X	X	X	
Archival tissue testing for PD-L1 expression and NGS f	X (After tissue pre-screen consent, prior to full informed consent, for patients enrolled under AM2)			
Blood for exploratory studies g		Cycles 1 and 2; q4 cycles beyond cycle 4 (C5, C9, etc.). Optional collection 1 week after cycle 1.	X	
Radionuclide bone scan and CT of abdomen/pelvis with contrast h	X	X (Prior to cycle 4 and every 3 rd cycle thereafter)		
Nivolumab administration		X		

Abbreviations: AE=adverse event; CBC=complete blood count; ECOG=Eastern Cooperative Oncology Group (performance score); EOS=end-of-study; mPca=diagnosis of metastatic prostate cancer; NGS=next-generation sequencing (e.g. Foundation One, OncoPanel).

- a Medical history: including relevant medical history collection, as well as Gleason score and TNM stage at diagnosis, results of any recent advanced imaging (Axumin, SPECT, choline, sodium fluoride, etc.)
- b Collect radiation site, administered dose per fraction and treatment duration, as well as any concurrent ADT and duration of ADT.
- c Physical examination includes height (at screening only), weight, vital signs, and general physical examination

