- d Blood chemistry panel includes sodium, potassium, chloride, bicarbonate, calcium, blood urea nitrogen, creatinine, alkaline phosphatase, total bilirubin, AST, ALT. Testosterone will be drawn during screening to confirm castration but does not need to be repeated after screening. CBC must include white blood cell differential. CBC and chemistry testing may occur up to 48 hours prior to day 1 of each cycle. Labs obtained on cycle 1, day 1 do not need to re-meet eligibility criteria. Treatment may begin at each cycle before TSH result is available.
- e See requirements for baseline PSA testing in inclusion criteria.
- f Results of PD-L1 testing (including confirmatory testing if positive) must be obtained so that subject can be assigned to a study cohort BEFORE starting study treatment. Following PD-L1 testing and NGS, remaining tissue will be used for exploratory studies.
- g Exploratory studies include germline whole-exome sequencing performed at baseline, peripheral immunophenotyping, soluble biomarkers, ctDNA, and T-cell collections at specified intervals. Please see appendix 3 for details of blood collection. Research blood specimens will generally be collected with monitoring labs detailed in footnote d above. If standard labs are collected in advance, then research blood samples may be collected on the treatment day (before or after treatment). If research blood samples are inadvertently missed during collection of standard labs just before treatment, then the research blood samples may also be drawn post-treatment (same day).
- h Radiographic imaging will be obtained after every 3rd cycle until EOS. Radiographic imaging includes CT abdominal/pelvis with contrast (or MRI if contraindication to intravenous contrast) and bone scan. Radiographic imaging may occur up to 8 days prior to day 1 of the upcoming cycle, or on day 1 itself. Baseline imaging may include advanced imaging modalities as described in the eligibility criteria, assuming there is no radiographic evidence of disease.

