### **12.3. Exploratory Analyses**

The exploratory analyses will proceed with all 34 enrolled patients combined if responses are observed. The markers of interest are described in Section 8.1. Some objectives will explore the relation among markers, and some will explore markers (e.g., PD-L1 expression, CD8+ TILs, change in plasma cytokines or PBMC subsets from pre-treatment to post-1 cycle) in relation to with disease control on nivolumab. With the given sample size and low expected disease control rate, all results will be considered as preliminary. Analyses will include descriptive and graphical summaries, using scatterplots and estimating correlation coefficients among continuous markers (including the % change in PSA at 12 weeks as continuous value), and using boxplots of marker levels according to the disease control endpoint. Hypothesis testing may be undertaken if there are several patients who experience disease control (more than say 4 or 5) of the hypothesis that greater expression of PD-L1 and/or CD8+ TILs is associated with higher probability of disease control, using Wilcoxon rank sum tests if the marker has a continuous distribution, or Fisher's exact test if an established cutpoint of the distribution exists.

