### Appendix 3: Instructions for peripheral blood collection for exploratory studies

As outlined in the study calendar (section 7), peripheral blood collections will be mandatory for subjects participating in this study.

- Cycle 1 day 1:
  - 5-10 mL in one 10-mL EDTA (purple top) tube at room temperature for germline WES
    - Email [name] ([[contact]](mailto:[contact])) in advance to notify [name] lab of collection
    - For DFCI patients, email BIDMC CRAs ([[contact]](mailto:[contact])) one week in advance to arrange collection
  - 30 mL in three-to-four 10-mL EDTA tubes at room temperature for soluble biomarkers and immunophenotyping
    - Email [name] ([[name]\\[contact]](mailto:[contact])) one week to notify Immune Assessment lab of collection
    - For BIDMC patients, blood will need to be brought to the Immune Assessment Lab by a BI CRA
    - For DFCI patients, blood can be sent via tube system
- Cycle 2 day 1 and End-of-Treatment visit, plus optional collection at 1 week after cycle 1:
  - 30 mL in three-to-four 10-mL EDTA tubes at room temperature for soluble biomarkers and immunophenotyping
    - Email [name] ([[name]\\[contact]](mailto:[contact])) one week to notify Immune Assessment lab of collection
    - For BIDMC patients, blood will need to be brought to the Immune Assessment Lab by a BI CRA
    - For DFCI patients, blood can be sent via tube system
- Cycle 5 day 1 and q4 cycles beyond (cycle 9 day 1, cycle 13 day 1, etc.):
  - 80 mL TOTAL in eight-to-eleven 10-mL EDTA tubes at room temperature, divided as follows:
    - 50 mL in five-to-seven 10-mL EDTA tubes at room temperature for PBMC banking for assessment of T-cell responsiveness to neoantigens
      - Email [name] ([[contact]](mailto:[contact])) in advance to notify [name]/[name] lab of collection
      - For DFCI patients, email BIDMC CRAs ([[contact]](mailto:[contact])) one week in advance to arrange collection
    - 30 mL in three-to-four 10-mL EDTA tubes at room temperature for soluble biomarkers and immunophenotyping PLUS PMBC banking for assessment of T-cell responsiveness to neoantigens
      - Email [name] ([[name]\\[contact]](mailto:[contact])) one week to notify Immune Assessment lab of collection

- For BIDMC patients, blood will need to be brought to the Immune Assessment Lab by a BI CRA
- For DFCI patients, blood can be sent via tube system

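### Footnote g of the study calendar allows the cycle 1 research blood to be drawn after the first nivolumab infusion, so some men may have no true pre-treatment value for the exploratory cytokine and PBMC analyses

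*Combined protocol and SAP*

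**What the plan says.** **Timing of the draw (Section 7, footnotes d and g).** The default is that "Research blood specimens will generally be collected with monitoring labs detailed in footnote d above". Footnote d adds that "CBC and chemistry testing may occur up to 48 hours prior to day 1 of each cycle". Footnote g then gives two permissions:

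- If standard labs were collected in advance, "research blood samples may be collected on the treatment day (before or after treatment".
- If the research tubes were overlooked when the standard labs were taken just before treatment, "then the research blood samples may also be drawn post-treatment (same day".

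**Schedule (Section 7 calendar; Appendix 3).** The on-treatment cell for exploratory blood reads "Cycles 1 and 2; q4 cycles beyond cycle 4 (C5, C9, etc", with an optional draw one week after cycle 1 and a further draw at end of study. The screening cell of that row is empty. For cycle 1 day 1, Appendix 3 asks for a germline sequencing tube and "30 mL in three-to-four 10-mL EDTA tubes at room temperature for soluble biomarkers and immunophenotyping". It does not say that either must be taken before the infusion.

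**Use of the samples (Sections 2.1.3 and 12.3).** One exploratory objective is to "Assess levels of plasma cytokines prior to initiation and during therapy"; a parallel one covers PBMC subsets, including their basal features. Section 12.3 names "change in plasma cytokines or PBMC subsets from pre-treatment to post-1 cycle" among the markers to be related to disease control.

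**The concern.** The objectives and Section 12.3 need a value measured before any nivolumab. The sampling rule does not guarantee one, and no other scheduled draw can replace it.

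The consequence is clearest for immunophenotyping. Section 1.3 describes high-affinity binding of nivolumab to activated human T-cells that express PD-1, so blood taken after the infusion contains the drug whose effect is being studied. For soluble markers the documents do not say whether levels move within hours of an infusion, so an effect there is possible but not shown.

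At stake is whether the pre-treatment term in Section 12.3 means the same thing for every man. A missed baseline cannot be collected later.

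**Working it through.** The plan states no figure on this point, so the check is a comparison of sections.

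1. **Do the permissions reach cycle 1?** Footnote g names no cycle in either permission. The first depends on labs being done early, and footnote d allows that for every cycle. The second depends on an oversight, which can happen at any cycle. Both can therefore apply at cycle 1.

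2. **Is the first permission only a rescue for accidents?** No. Once labs have been done early, it leaves before or after treatment as a free choice.

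3. **Is there a backup pre-treatment draw?** No. Screening has none. The optional one-week draw, cycles 2, 5, 9 and onward, and end of study all follow the first dose.

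4. **Is a pre-dose rule restored elsewhere?** Not in Appendix 3, Section 8 or Section 12.3. Footnote f does require PD-L1 results before treatment starts, so the calendar states such a condition when it is intended.

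5. **Could the analyst identify an affected sample?** Not from the label. Under Section 8.4 it carries the enrollment number, initials, protocol number and cycle number. No section asks for draw time relative to the infusion.

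6. **How many men?** The share *f* of cycle 1 samples drawn after the infusion is not given. With 34 planned patients (Section 12.1), the number with a true pre-treatment sample is 34 × (1 − *f*). The values of *f* below are assumptions that span the whole possible range; the documents favour none of them.

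| Assumed *f* | 34 × (1 − *f*) |
|---|---|
| 0% | 34 |
| 10% | 30.6 |
| 25% | 25.5 |
| 50% | 17 |
| 100% | 0 |

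7. **Cycle 2.** The same footnote leaves the cycle 2 draw before or after the second infusion, so the change score has four possible timing patterns (2 × 2). The two ends are not equally serious. Section 1.5 gives a geometric mean half-life of 26.7 days and Section 5.2 a 28-day cycle. On simple exponential decay, the fraction of the first dose left at cycle 2 is 0.5^(28/26.7) = 0.5^1.049 ≈ 0.48. This is a rough figure, since the half-life has a CV of 101%, but it shows that drug is present at cycle 2 on either side of the infusion. At cycle 1 the contrast is between no drug and drug.

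**The case against.** The best defence is that the default already does what is needed. Research blood goes with the monitoring labs, which precede the dose, and a draw after treatment is permitted but never required. Section 12.3 speaks of a pre-treatment value, so a sample known to be post-infusion would not qualify as written. Section 8.1 calls the work hypothesis-generating and conditional on responses being seen, and Section 12.3 treats all results as preliminary. Whether a man is affected would follow from site logistics, which suggests added noise more than bias related to outcome.

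Most of this stands and limits the size of the point. It does not remove it: the default is worded as what generally happens, and excluding a post-infusion sample depends on knowing its timing, which nobody is asked to record.

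A reader might infer several stronger things that the documents do not support:

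- **That the biomarker objectives lose their baseline outright.** Only men drawn after the infusion under a permission are affected.
- **That one or two bad baselines could distort the hypothesis tests foreseen when more than about 4 or 5 men have disease control.** Those tests concern PD-L1 and CD8+ TILs in tumour tissue, which the blood draw cannot affect. No test is specified for cytokines or PBMC subsets.
- **That premedication contaminates the cycle 1 sample.** Section 6.6 recommends it only for infusions that follow a reaction.
- **That post-infusion cycle 2 samples are invalid.** Drug is already on board by then, so excluding them all would discard data on weak grounds.
- **That T-cell banking at cycle 1 is compromised.** Appendix 3 schedules PBMC banking only from cycle 5.

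**Conclusion.** The gap is real and minor. As written, a site can follow footnote g exactly and take the only potential pre-treatment research sample after the first infusion, while Sections 2.1.3 and 12.3 rely on a value from before treatment. The number of men affected is unknown: zero is possible, 34 is the ceiling, and the documents give no basis for a figure in between.

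The effect is confined to the exploratory soluble-marker and immunophenotyping summaries. The primary and secondary endpoints, tissue markers, germline sequencing and the PD-L1/TIL tests in Section 12.3 are untouched. The conclusion assumes that no instruction outside these documents, such as a laboratory manual, already imposes a pre-dose draw.

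**What to change.** Amend footnote g and Appendix 3 so that:

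- the cycle 1 soluble-biomarker and immunophenotyping tubes are drawn before the first infusion, on the day or within the existing 48-hour lab window;
- the after-treatment allowance stays for the germline tube and for later cycles;
- draw time and infusion start are recorded at cycles 1 and 2.

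Add to Section 12.3 that a post-infusion cycle 1 sample is not used as the pre-treatment value. At cycle 2, prefer a pre-infusion draw, and flag post-infusion samples (for example in a sensitivity summary) instead of excluding them. If samples have already been taken, recover draw and infusion times from source records where possible.

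The cost is a wording change and two recorded times per visit, with no extra blood or visits. The downside is that an occasional cycle 1 value becomes missing.

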### **2.1.2. Secondary Objectives**

- Determine the maximal change (proportional) and best decline (absolute) in prostate specific antigen (PSA) during nivolumab treatment
- Describe the change in PSA doubling time (PSADT) during nivolumab therapy relative to baseline
- Determine the time to development of overt metastatic disease after treatment with nivolumab
- Determine the time to initiation of androgen deprivation therapy (ADT) after treatment with nivolumab
- Assess the toxicity of nivolumab monotherapy in patients with BCR PCa

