### **2.2.2. Secondary Endpoints**

- Maximal change in prostate specific antigen (PSA) during nivolumab treatment, as a percentage of baseline
- Best PSA response during nivolumab treatment, as an absolute change relative to baseline
- Change in PSA doubling time (PSADT) at end-of-study relative to baseline
- Time from enrollment to PSA progression (10% or greater increase in PSA relative to baseline)
- Time from enrollment to development of radiographic metastatic disease
- Time from enrollment to initiation of ADT
- Safety of nivolumab

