## 6.7. Protocol Therapy Discontinuation

In addition to discontinuation from therapy related to toxicities as outlined above, a subject will also be discontinued from protocol therapy and followed per protocol under the following circumstances outlined below. The reason for discontinuation of protocol therapy will be documented on the electronic case report form (eCRF).

The Prostate Cancer Working Group 3 (PCWG3) recognizes that favorable effect of experimental therapies on PSA may be delayed for  $\geq 12$  weeks and recommends continuing treatment through early rises for a minimum of 12 weeks unless there is other evidence of progression.

PCWG3 recommends continuing experimental therapies for subjects who experience PSA rise after initial decline, in the absence of any radiographic or clinical progression. However, subjects in this trial do have access to a standard-of-care treatment in the form of ADT which can be used to delay development of metastatic disease, although a convincing survival benefit has not been established in this setting. This trial requires treatment discontinuation only for the reasons below, but investigators are advised to use discretion for patients with rapidly increasing PSAs (after 12 weeks of treatment). Patients believed to be clinically benefitting, for example based on decreased PSADT after starting nivolumab, could be continued on treatment at the investigator's discretion.

- Documented metastases on imaging (see Section 9 for definitions).
- Completed 2 years of treatment with nivolumab
- Site investigator determines a change of therapy (i.e. starting ADT) would be in the best interest of the subject
- Subject or legal representative (such as a parent or legal guardian) withdraws consent and requests to discontinue protocol therapy, whether due to unacceptable toxicity or for other reasons
  - In a subject decides to prematurely discontinue protocol therapy (“refuses treatment”), the subject should be asked if he or she may still be contacted for further

scheduled study assessments. The outcome of that discussion should be documented in both the medical records and in the eCRF.

- Unacceptable adverse experiences
- Intercurrent illness that prevents further administration of treatment
- Protocol therapy is interrupted for > 6 weeks (calculated from the date of the first missed dose). Any potential exceptions to this criteria must be discussed with and approved by the PI.

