- i End of study (EOS) assessments should be conducted in-person within 30 days after the last dose of nivolumab. AEs will also be assessed at 100 days after the last dose of nivolumab in the Follow-up Period (see footnote l). Patients must contact the study team regarding any significant toxicities or illnesses that occur within 100 days of last nivolumab dose, as SAEs must be reported during this time. For patients experiencing toxicities, EOS visits should occur every 2 weeks ( $\pm$  3 days) until toxicities resolve. Depending upon the toxicity, the every 2-week assessment may be accomplished via phone call, email or other avenues as appropriate. Mode of assessment will be at site investigator's discretion.
- j All visits have a window of  $\pm$  3 days.
- k Baseline imaging may be performed up to 60 days prior to enrollment.
- l Follow-up period will continue until documentation of metastatic disease (via radiographic imaging and/or biopsies). Follow-up may consist of medical record review (for patients treated at BIDMC) or contact via phone/email (for patients treated at non-BIDMC institutions). Data to be collected includes: date of initiation of any subsequent hormonal therapy, date of documented metastatic disease, and any other therapies received during follow-up period. If contact is made via phone/email with patient, then written documentation must be provided to confirm these dates and the diagnosis of metastatic disease. In addition, the research nurse must attempt to contact the patient (via phone or email depending on patient preference) approximately 100 days after the

last dose of nivolumab, +/- 1 week, to assess AEs. If the patient cannot be reached, attempts should be documented in the medical record and this will not be considered a deviation from protocol.

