#### **12.2.2. Secondary analysis and analysis of safety**

Maximum PSA change and best PSA response will be summarized descriptively and graphically in waterfall plots. PSA doubling time will be calculated with linear regression model of natural logarithm of PSA and time. PSADT at baseline and

EOS will be summarized, and change in PSADT, as captured by the change in PSA slope, will be summarized descriptively as well. Time to event endpoints will be summarized using Kaplan Meier estimate.

All reported toxicities, regardless of attribution, will be summarized by toxicity type and maximum grade. The maximum grade consolidates the reports of a given toxicity for a patient over time by taking the maximum across time. Immune modulatory medication used for toxicities will also be summarized descriptively.

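### Follow-up stops at metastasis while time to ADT is a secondary endpoint, so ADT started because of metastasis is not systematically recorded and the Kaplan-Meier estimate is pushed upward

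*Combined protocol and SAP*

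**What the plan says.** - Section 2.1.2 lists as a secondary objective: "Determine the time to initiation of androgen deprivation therapy (ADT) after treatment with nivolumab". Section 2.2.2 gives the endpoint as "Time from enrollment to initiation of ADT". Neither limits it to ADT begun before metastasis.
- The follow-up column of the Section 7 calendar reads "Every 3 months until mPCa", and footnote l repeats the stopping point: "Follow-up period will continue until documentation of metastatic disease (via radiographic imaging and/or biopsies".
- Footnote l also lists what follow-up collects: "Data to be collected includes: date of initiation of any subsequent hormonal therapy, date of documented metastatic disease, and any other therapies received during follow-up". The list belongs to a follow-up period that closes at metastasis.
- Section 6.7 makes metastasis a reason to stop nivolumab: "Documented metastases on imaging (see Section 9 for definitions". A man whose metastasis is found on treatment has therefore met the follow-up stopping rule by the time he leaves treatment.
- Section 12.2.2 gives the whole analysis: "Time to event endpoints will be summarized using Kaplan Meier estimate". It says nothing on censoring or competing events.

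**The concern.** Kaplan-Meier assumes that a censored man has the same future chance of the event as those still under observation. Section 1.1 describes holding ADT back until metastases appear as one recognized strategy, so a man with new metastases and no ADT is more likely than average to start it soon. If his record closes at metastasis, he leaves the risk set just before the event, and the curve behaves as though his chance of ADT were that of a man without metastases. The estimated time to ADT is then too long, which favors nivolumab. Section 1.9 names delaying the need for ADT among the questions this trial should help to answer, and Section 9 cites it as part of the reason for counting PSA stabilization in the primary endpoint. Historical readers of the curve would take it as evidence on that question.

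**Working it through.** **The plan's own figures.** The documents give no figure for time to ADT. Their numerical design claims concern the primary endpoint and reproduce by exact binomial calculation. For n = 20 with success at 2 or more, alpha is 0.0169 at a 1% rate and power is 0.976 at 25% (stated 0.02 and 97%). For n = 14 with success at 1 or more, alpha is 0.131, power is 0.956 at 20%, and the chance of no responders is 0.044 (stated 0.13, 96% and 4.4%). This point does not touch them.

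**Which contacts remain after metastasis.**
- *Metastasis found on treatment.* Scheduled scans fall on day 1 of the next 28-day cycle or up to 8 days before it, that is, 20 to 28 days after the last dose. The end-of-study visit, which includes a medication review, is due within 30 days of the last dose. That leaves 30 - 28 = 2 to 30 - 20 = 10 days in which an ADT start could be seen. The contact at about 100 days is for adverse events, and a documented failed attempt is not a deviation.
- *Metastasis found in follow-up.* The record review or 3-monthly contact that documents metastasis can pick up ADT begun before that contact. No later contact for ADT is required.

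**Upper bound.** Let a be the constant hazard of ADT before metastasis, m the constant hazard of metastasis, and f = m/(a + m) the share reaching metastasis first. If ADT starts at metastasis, the true median time to any ADT is ln 2/(a + m). Kaplan-Meier censored at metastasis estimates ln 2/a. The ratio is (a + m)/a = 1/(1 - f):
- f = 10%: 1/0.90 = 1.11
- f = 30%: 1/0.70 = 1.43
- f = 50%: 1/0.50 = 2.0

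**Allowing for a lag and partial capture.** This is a simulation of 200,000 men. Every rate is an assumption, because the documents give none: median time to pre-metastatic ADT 18 months; median time to metastasis 18, 36 or 72 months; ADT following metastasis after an exponential lag with mean 1 or 2 months; independent exponential times. Entries are medians in months, with the excess over full ADT follow-up in brackets.

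| Median to metastasis | Mean lag | f | Full ADT follow-up | Censored at metastasis | Stopped at next 3-monthly contact | Post-metastasis starts captured by that contact |
|---|---|---|---|---|---|---|
| 18 | 1 | 0.50 | 9.5 | 17.9 (+88%) | 10.9 (+15%) | 70% |
| 18 | 2 | 0.50 | 10.1 | 18.0 (+78%) | 12.6 (+25%) | 50% |
| 36 | 1 | 0.34 | 12.3 | 18.0 (+46%) | 13.5 (+10%) | 69% |
| 36 | 2 | 0.33 | 12.7 | 18.0 (+42%) | 14.7 (+16%) | 50% |
| 72 | 1 | 0.20 | 14.6 | 18.0 (+23%) | 15.5 (+6%) | 70% |
| 72 | 2 | 0.20 | 14.9 | 18.1 (+21%) | 16.3 (+9%) | 49% |

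The strict-censoring excess stays below the bound (2.0, 1.5 and 1.25 for f of one half, one third and one fifth) because of the lag. Censoring at metastasis returns about 18 months in every row: it estimates the pre-metastatic ADT hazard alone, whatever the metastasis rate.

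**The case against.** A reader might infer that ADT given for metastasis is never recorded. The documents do not support that. Footnote l asks for the date of any later hormonal therapy alongside the metastasis date, and the 3-monthly contact, the record review and the end-of-study medication review can each catch some starts. What stands is that capture is left to timing.

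Nor does the plan say that men are censored at metastasis. That is inferred from where data collection ends, because Section 12.2.2 is silent. The silence is itself a gap, and it leaves the estimand open. If the sponsor meant ADT before metastasis only, metastasis would be a competing event and one minus Kaplan-Meier would overstate the incidence of ADT, an error in the other direction. The endpoint as worded covers any ADT, so too long is the right direction here, but either reading needs a rule.

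A doubling of the median is also tempting to quote. It needs half the men to reach metastasis first, ADT to start that day, and no capture. The protocol expects some men to start ADT earlier: Section 1.1 notes its use at short PSA doubling times, and Section 6.7 lets the investigator stop nivolumab for it.

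A reader might further infer that running the clocks from enrollment builds in event-free time while PD-L1 is typed. Section 5.1 undercuts this: early on, treatment may start before typing, and once the negative cohort closes, typing precedes full consent. The baseline for PSA progression is not clearly fixed at cycle 1 day 1 either. That is not part of this point.

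Finally, this is a descriptive endpoint in 34 men with no comparator, test or decision rule, and Section 1.9 looks to a larger trial to settle the question of delaying ADT. That limits the consequence but does not remove the bias.

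**Conclusion.** The point holds in a limited form. Data collection is required only up to metastasis, the endpoint is any ADT, and metastasis raises the chance of ADT. Treating uncaptured men as censored there is informative and makes time to ADT too long. The direction rests on the endpoint as worded and on ADT commonly following metastasis.

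The size cannot be derived from the documents. The bound 1/(1-f) gives 1.11 to 2.0 for an assumed f of 10% to 50%. Under the simulated rates the excess is about 20% to 90% (3 to 8 months) with strict censoring, and about 6% to 25% (1 to 2.5 months) if the next 3-monthly contact records ADT. It would be smaller if few men reach metastasis first. The primary analysis and sample size are unaffected, but the change is worth making because it is cheap.

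**What to change.** 1. Amend footnote l and the calendar column so that record review or phone/email contact continues for the ADT start date until ADT starts, whether or not metastasis has been documented.
2. State in Section 12.2.2 that metastasis does not censor time to ADT, and that men without ADT are censored at the last contact at which their ADT status was known.
3. Add time to the first of ADT or metastasis to Section 2.2.2 and report it alongside. The dates already collected support it, and follow-up ending at metastasis does not bias it in this way.

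The cost is one extra date per man with metastasis, through contact routes the plan already uses, though more than one check may be needed where ADT is deferred. No visits or tests are added.
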